9.4 Data analysis plan

Primary analysis will be conducted by the intention to treat principle. Categorical variables will be expressed as frequencies and percentages. For continuous variables, a Shapiro-Wilk test of normality will be performed, and normally distributed data will be presented as means ± SD, while non-normally distributed data will be presented as median and interquartile range (IQR). However, the literature will be reviewed to ensure that variables are handled in their natural form. The effect of IV iron (vs. oral iron) on the primary endpoint (anemia at six weeks post-partum) would be analyzed using log-binomial regression models to obtain relative risks, 95% confidence intervals and p-values. The extent to which inclusion of baseline covariates modifies the precision of estimates would be explored. Generalized linear mixed models will be used to estimate the effect of treatment arm on repeated measures of hemoglobin and iron status biomarkers. The proportions of participants in the treatment arms who are anemic or iron deficient, and the proportions of participants who achieve anemia correction at 6 weeks and 6 months follow-up with be compared. Kaplan Meir plots and log-rank test will be used to explore the time to anemia correction. Subgroup analysis will be conducted to compare study findings by mode of delivery (caesarean vs vaginal delivery), and by the occurrence of primary post-partum hemorrhage. Two tailed test of hypothesis and 95% confidence interval is assumed as statistical level of significance. Stata version 17 (Stata Corp, Texas, USA) statistical software will be utilized for analysis. The variance estimator with cluster option (clustering on site of study) will be utilized.

Interim analysis will be conducted after achieving half of the sample size. Based on O'Brien-Fleming method (29), the threshold for significance of the primary endpoint at the interim analysis will be alpha = 0.0054. The clinical trial is terminated if the null hypothesis is rejected. The alpha level for the analysis at the end of the study will be adjusted to 0.0492 based on alpha adjustment based on O'Brien-Fleming method.

Interim analysis will also be performed to adjust the sample size, if necessary, as part of an adaptive study design. This will be a blinded analysis and its aim is to determine the actual effect size of the primary outcome in order to adjust the sample size if required. This will be performed by an independent body, and not the study co-investigators.

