4.1 Study setting and site selection

The study will be undertaken in four states in Nigeria, two states in the North - Kano and Kwara states, and two in the South - Lagos and Rivers states. North-South differentials in the use of maternal health services, and in maternal health indices, such as lower ANC attendance and poorer maternal-infant outcomes in the North (14, 24, 25) necessitated representation of both regions in this study. The variation in indices across the four states strengthens the rationale for their selection. Lagos has the highest proportion of women with 4 or more ANC contacts as per the most recent guidelines of the World Health Organization. Kano has one of the least in the country while Rivers and Kwara reflect the average number of ANC contacts for many states in Nigeria. In terms of existing infrastructure, number of health facilities range from 994 in Kwara to 2,333 in Lagos (Figure 1).

Source of data for map: 2021 projected population by the National Bureau of Statistics, 2017 demographic Statistics Bulletin by National Bureau of Statistics, 2018 Nigerian Demographic Health Survey, 2020 Nigeria Health Facility Registry

Figure 1: Map of Nigeria indicating the four selected states for the study with key population and service indices

Five (5) health facilities at the three levels of health care (primary, secondary, and tertiary health facility) will be selected from each state for this study, making a total of twenty (20) study sites for this study (one tertiary, three secondary and one primary healthcare facility). The facilities are selected with consideration for antenatal patient flow, number of deliveries and proximity of all three levels of care to facilitate an effective two-way referral system (Table 1). Each state will have a Principal investigator (PI)

and each site will have a clinician as Site Coordinator (SC) and two research nurses. Eligibility criteria applied for site selection at all the states include:

- Exclusively publicly funded primary, secondary or tertiary health facility
- Presence of an antenatal clinic that serves at least 60 pregnant women per month and a labor ward that provides deliveries for at least 20 women per month
- Presence of a labor ward that provides consistent 24-hour vaginal delivery services

Table 1: Study sites and codes

Site code	State	Name of Study Site					
01	Lagos	Lagos University Teaching Hospital (LUTH), Idi-Araba, Lagos					

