4.3 Sample size

We will enroll 1400 women into the trial. Power calculations assume a 1:1 randomization ratio to each of the two treatment groups.

For the primary outcome (anemia), we used data from a recent meta-analysis (28), which reported that 39% of women were anemic at six weeks postpartum. A sample size of 697 participants per arm would

^{**}A prospective participant with chronic medical condition (e.g HIV infection) will not be excluded unless there are contra-indication for the use of iron supplementation.

provide 90% power to detect to detect a relative reduction of 20% for IV iron to reduce the event rate of anemia at six weeks postpartum to 30%, after accounting for 10% loss to follow-up.

Bearing in mind the proposed one-time interim analysis to be conducted by the Data and Safety Monitoring Board (DSMB) at mid recruitment, we applied the O'Brien-Fleming rule (29), adjusting our final alpha level to 0.0492 (*See section 9.3 for interim rule*), which increased our final sample size to 1400 (700 per arm of the study).

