4.4 Randomization

Randomization and enrolment will occur between six and 48 hours after delivery and the initial post-delivery blood loss. Postpartum women during this window (6-48 hours postpartum) will be screened, enrolled, and randomized to one of the two treatments groups. Individual randomization and allocation concealment will be done with the use of a web-based randomization software known as 'Sealed envelope' in a 1:1 ratio in blocks stratified according to study site (Table 1). Screening, consenting, enrolment and randomization will be done by dedicated and trained study research nurses/midwives at each participating study site.

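### A site-clustered variance on only 20 sites, with no small-sample reference stated, would make the primary confidence interval too narrow and the interim stopping test too liberal

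*Protocol*

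**What the plan says.** - **Unit of randomisation (4.4).** Women are randomised individually, "in a 1:1 ratio in blocks stratified according to study site". Both arms therefore occur within every site.
- **Number of sites (4.1).** Five facilities in each of four states, "making a total of twenty (20) study sites for this study". Each state has one tertiary, three secondary and one primary facility. No planned enrolment per site is given.
- **Primary model (9.4).** The effect on anemia at six weeks "would be analyzed using log-binomial regression models to obtain relative risks, 95% confidence intervals and p-values". The covariate sentence is separate: "The extent to which inclusion of baseline covariates modifies the precision of estimates would be explored". It names neither site nor baseline hemoglobin.
- **Variance (9.4).** "The variance estimator with cluster option (clustering on site of study) will be utilized". The sentence is not limited to any one analysis, so on a plain reading it covers the primary model. No small-sample correction and no t reference is mentioned.
- **Error levels.** The sample size section (4.3) describes "adjusting our final alpha level to 0.0492". Section 9.4 says "the threshold for significance of the primary endpoint at the interim analysis will be alpha = 0.0054", and rejection at that look ends the trial. Tests are two-sided with 95% intervals.

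**The concern.** Clustering on site is needed when sites are the units of assignment. Here they are not: treatment is balanced within each site by design, so site is a factor to adjust for. A site-clustered sandwich variance discards the information from about 1,260 individual outcomes and estimates the variance from 20 site-level sums. Such an estimate is itself noisy and tends to run low when sites differ in size. Comparing the resulting statistic with normal critical values ignores that noise.

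Three things are at stake: the primary p-value, the primary confidence interval and the interim stopping decision. The error grows towards the tail, so it is proportionally worst at the stringent interim threshold. The protocol moves its final level from 0.05 to 0.0492, a change of 0.0008, to protect the overall error rate. An excess of one to two percentage points from the variance estimator would far outweigh that adjustment.

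**Working it through.** **Inputs from the protocol.** 1,400 women, 1:1, 20 sites; 10% loss, so 1,400 x 0.9 = 1,260 evaluable at the end and 700 x 0.9 = 630 at the halfway look; 39% anemic under no effect; two-sided levels 0.0492 and 0.0054.

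**Inputs assumed, not in the protocol.** A normal reference for the clustered statistic; site sizes from equal to moderately unequal (coefficient of variation, CV, 0 to 0.75); site effects with SD 0.5 on the logit scale; baseline hemoglobin effect 0.7 logit per SD; blocks of 4.

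**Step 1: analytic check.** With G equal-sized clusters the statistic behaves roughly like t on G - 1 = 19 degrees of freedom. The normal critical values are 1.967 (for 0.0492) and 2.782 (for 0.0054). Two-sided tail areas under t(19):

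- beyond 1.967: 0.064, against 0.0492;
- beyond 2.782: 0.0119, against 0.0054, a ratio of 2.2.

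**Step 2: null simulation.** The estimate is log RR = log(p1/p0) from the two-arm log-binomial model. Its clustered variance is V = G/(G - 1) x sum over sites of (sum of psi within the site) squared. Here psi = (y - p1)/(n1 p1) in the intervention arm and -(y - p0)/(n0 p0) in the control arm. The comparator is a site-adjusted linear model with the baseline covariate and individual-level robust variance. There were 20,000 trials per row.

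| Site sizes | Clustered, final (0.0492) | Clustered, interim (0.0054) | Clustered, either look | 95% CI coverage | Site-adjusted, final |
|---|---|---|---|---|---|
| Equal | 0.063 | 0.011 | 0.068 | 93.6% | 0.050 |
| CV 0.50 | 0.065 | 0.011 | 0.071 | 93.4% | 0.047 |
| CV 0.75 | 0.074 | 0.016 | 0.082 | 92.5% | 0.048 |

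The two stated levels together imply an overall error of 0.0513. The site-adjusted test gave 0.049 to 0.053 over both looks. Separate runs without the covariate gave 0.062 to 0.064 (equal sites) and 0.067 to 0.069 (sites 6:3:3:2:1 within each state) at the end. At the interim they gave 0.011 to 0.012 and 0.013 to 0.014. A site-stratified Mantel-Haenszel relative risk held 0.047 to 0.050 and 0.0044 to 0.0056.

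**Step 3: does t(19) repair it?** Replacing normal by t(19) critical values at both looks brings the overall error to 0.051 (equal), 0.053 (CV 0.50) and 0.062 (CV 0.75). This largely repairs it, but not fully when sites are quite unequal.

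**Step 4: what the missing covariates do.** With an ordinary model-based variance the unadjusted test is slightly conservative: 0.043 to 0.044 at nominal 0.0492, with a standard error about 2 to 4% too large. Adding site and baseline hemoglobin while keeping the clustered variance and normal reference leaves the error at about 0.06 to 0.07. The excess therefore comes from the variance estimator and its reference distribution. On precision, for an assumed correlation of 0.2 to 0.5 between baseline and six-week hemoglobin, adjustment cuts the variance by about 3 to 13%. It raises power for 39% against 31.2% (0.39 x 0.8) from about 82-83% to 84-87%. At the protocol's other figure, 30%, power is already about 91.9% with 627 evaluable per arm, so there is less to gain.

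**The case against.** - **The protocol does not state a normal reference.** This stands. It is a software default assumed here, and a statistical analysis plan that is not shown could name a correction. But the protocol does choose the clustered estimator, and as written nothing guards against the small number of sites.
- **Site sizes are unknown.** This stands for the size of the excess, though not its direction. A reader might infer that false early stopping becomes more than three times as likely as stated. That needs a strongly uneven site pattern, for which the protocol gives no basis; equal to moderately unequal sites give about two to three times.
- **Missing covariates.** A reader might infer that leaving out site and baseline hemoglobin also narrows the interval. Step 4 shows that it does not. Nor is the primary estimate undefined: the natural reading of 9.4 is an unadjusted primary analysis with adjustment explored. An unadjusted analysis is valid in a randomised trial, and restricting entry to hemoglobin of 9.9 g/dl or less limits what baseline hemoglobin can explain.
- **Clustering may be deliberate.** This is the strongest point. Sites span three care levels and four states, so the treatment effect may vary by site. With a zero average effect and assumed site-varying log-odds effects (SD 0.2 to 0.4), the site-stratified test rejected 0.066 to 0.113 of the time with equal sites and 0.070 to 0.132 with 6:3:3:2:1. Clustered variance gave 0.060 to 0.071 with a normal reference and 0.046 to 0.055 with t(19). If inference is meant for a wider population of sites, clustering with a proper reference is defensible. If it is meant for these 20 sites, the stratified test is valid under no effect at any site. A reader should not conclude that clustering must be removed outright.

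**Conclusion.** The concern holds in a limited form. A site-clustered variance with 20 sites, used with normal critical values and no correction, gives a primary interval with coverage of about 92.5 to 93.6%. Type I error is about 0.062 to 0.074 in place of 0.0492, and about 0.011 to 0.016 in place of 0.0054 at the look that can stop the trial. The final-look excess is modest; the interim excess is proportionally larger, at two to three times the stated level. These figures rest on the assumed normal reference and on site sizes between equal and a CV of 0.75. The direction does not depend on the assumed site effects. The absence of site and baseline hemoglobin from the primary model is a separate, smaller matter of efficiency.

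**What to change.** State the primary model as treatment, site (the randomisation stratum) and continuous baseline hemoglobin, reporting a relative risk with an individual-level robust variance. If small sites prevent convergence, use a site-stratified Mantel-Haenszel relative risk.

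If the site-clustered variance is kept, whether as the primary method or as a sensitivity analysis allowing for treatment-by-site variation, specify a small-sample correction and a t reference on about 19 degrees of freedom. Say which population of sites the inference is meant for, and apply the same method at the interim and final looks.

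The cost is wording in the protocol or analysis plan, settled before the interim data are seen. No new data are needed, since baseline hemoglobin is measured in every woman at screening. The downsides are that an individual-level variance supports inference to these sites only, and that very small sites may have to be merged.

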10 STUDY MONITORING PLAN

10.1 Monitoring and evaluation (M & E) mechanism

The Project monitoring and evaluation mechanism will help to determine progress being made towards achievement of study outcomes and will provide constructive recommendations to address key problems identified. It will review the effectiveness, efficiency, and timeliness of project implementation; analyze effectiveness of implementation and partnership arrangements; identify issues requiring decisions and remedial actions; analyze whether the project is on track with respect to achieving the expected results; and propose any mid-course corrections and/or adjustments to the Work Plan as necessary.

The project M&E mechanism will include

- An Administrative Core- this will be the essential infrastructure that will enable synergy and coordination of the project, scientific core, and the collaborating sites of IVON-PP. The administrative core will consist of the Chief Investigator, a project manager, a project officer, other administrative staff. They will provide administrative oversight and management of the research study and coordinate all internal and external meetings of investigators, staff, and monitors.
- The full research team consisting of the CI, Co-Is, State PIs and administrative core will hold a biweekly meeting via zoom platform.
- The Trial Steering Committee (TSC) will meet (in person ideally) prior to commencement of the accrual and then at a minimum of once yearly (in person or remotely) and will provide independent oversight of the trial and associated studies on behalf of the trial sponsor.
- The Data Safety and Monitoring Board (DSMB) will meet (in person ideally) prior to commencement of the accrual and then at a minimum of once yearly (in person or remotely) to independently assess safety, effectiveness and futility of the trial and will report to the TSC. Full details of both the TSC and DMC will be outlined in a charter.
- The DSMB will review the prevalence of serious adverse events with the possibility of either continuing or stopping the trial. The details for the operation and responsibilities of the DSMB will be provided in the DSMB operational protocol/charter.
- Clinical Trial Monitors Independent clinical research associates/monitors will be responsible for trial monitoring. To verify that: (a) the rights and well-being of human subjects are protected. (b)

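### The interim and final levels of 0.0054 and 0.0492 have the O'Brien-Fleming shape but the wrong constant, so the overall error is 5.13%; the look is also not tied to six-week results

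*Protocol*

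**What the plan says.** Section 9.4 places an interim analysis at half the sample size. It introduces the rule with "Based on O'Brien-Fleming method (29" and continues: "the threshold for significance of the primary endpoint at the interim analysis will be alpha = 0.0054". It then says "The clinical trial is terminated if the null hypothesis is rejected", so the interim is a true efficacy look that spends error. For the end of the trial: "The alpha level for the analysis at the end of the study will be adjusted to 0.0492". The overall level is two-sided 5%: "Two tailed test of hypothesis and 95% confidence interval is assumed as statistical level of significance".

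Section 4.3 describes the same look as "the proposed one-time interim analysis to be conducted by the Data and Safety Monitoring Board (DSMB) at mid recruitment" and repeats the final level ("adjusting our final alpha level to 0.0492"). It uses that level to go from 697 to 700 women per arm. The primary outcome (section 3.1.1) is read at six weeks postpartum, and the synopsis gives that visit a window of one week either side.

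**The concern.** The protocol fixes two exact thresholds for its confirmatory test, attributes them to a named method and implies that together they keep the two-sided 5%. If they do not belong together, the decision rule is wrong as written. The final level appears in two sections and enters the sample size, so it is not a slip in a single line.

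Fixed nominal levels are also exact only at the information fraction they were derived for. Here information on the primary outcome accrues with six-week hemoglobin results, about six weeks behind enrollment. A look timed by enrollment alone would fall short of one half.

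**Working it through.** **Inputs.** Interim level 0.0054 and final level 0.0492 (section 9.4); two-sided 5% overall (section 9.4); one look at one half (sections 9.4 and 4.3); 697 then 700 per arm, 90% power, 39% versus 30% anemic, 10% loss (section 4.3); six-week outcome with a window of 5 to 7 weeks (section 3.1.1 and synopsis).

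**1. The plan's own sample-size step.** Rescaling 697 from a level of 0.05 to 0.0492 at 90% power:

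697 × [(1.9669 + 1.2816) / (1.9600 + 1.2816)]² = 700.0.

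This reproduces the stated 700, so 0.0492 was indeed the level used.

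**2. Shape of the stated pair.** The critical values are z₁ = Φ⁻¹(1 − 0.0054/2) = 2.782 and z₂ = Φ⁻¹(1 − 0.0492/2) = 1.967. Their ratio is 1.4145, essentially √2 = 1.4142. That is the O'Brien-Fleming relation z₁ = c/√0.5, z₂ = c, with c = 1.967.

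**3. The constant that keeps 5%.** With information fraction t, (Z₁, Z₂) is bivariate normal with correlation √t under the null. Solve

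P(|Z₁| > c/√0.5 or |Z₂| > c) = 0.05 at t = 0.5.

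The solution is c = 1.977, so z = 2.797 and 1.977, and the nominal levels are 0.0052 and 0.0480.

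**4. Overall error of the stated pair at one half.**

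P(|Z₁| > 2.782 or |Z₂| > 1.967) = 0.0513.

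The plain sum, 0.0054 + 0.0492 = 0.0546, overstates the error because the two statistics are correlated.

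**5. Can one of the two levels be kept?** With 0.0054 at the interim, the final level must be 0.0479. With 0.0492 at the end, the interim level can be at most 0.0026. The Lan-DeMets O'Brien-Fleming-type spending function (0.025 on each side) gives 0.0031 and 0.0490 at one half. None of these gives the stated pair.

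**6. Timing.** The protocol gives no accrual duration, so 12 and 24 months of even accrual are assumptions. If data are cut when the 700th woman is enrolled, the number still awaiting the six-week visit is (1400 / months) × (lag in weeks / 4.348). The information fraction is t = (700 − waiting) / 1400; equal loss before and after the look cancels.

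| Accrual (months) | Lag (weeks) | Waiting | With result | t | Overall error, stated levels |
|---|---|---|---|---|---|
| 12 | 5 | 134 | 566 | 0.40 | 0.0519 |
| 12 | 6 | 161 | 539 | 0.39 | 0.0521 |
| 12 | 7 | 188 | 512 | 0.37 | 0.0522 |
| 24 | 5 | 67 | 633 | 0.45 | 0.0516 |
| 24 | 6 | 80 | 620 | 0.44 | 0.0517 |
| 24 | 7 | 94 | 606 | 0.43 | 0.0517 |

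If instead the analysis waits for the first 700 women's six-week visits, then after 10% loss t = 630/1260 = 0.5, and the error is the 0.0513 of step 4.

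**7. Cost of correcting the final level.** With 630 evaluable women per arm (700 × 0.9), comparing two proportions at the final analysis: for 39% versus 30%, power goes from 0.919 to 0.918. For 39% versus 31.2% (the literal 20% relative reduction also named in section 4.3), it goes from 0.826 to 0.823. Rescaling 697 as in step 1 to a level of 0.0480 gives 704.5, so 705 per arm instead of 700.

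**The case against.** The strongest reply is size. The interim level is off by 0.0002 and the final level by 0.0012. The pair has the right shape, and the Lan-DeMets final level (0.0490) is only 0.0002 from the stated one. All of this stands: it makes the matter a calibration error, not a threat to the trial's conclusion. It does not make the levels correct.

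On timing, section 9.4 does not say that the trigger is recruitment. Since the Primary Analysis set in section 9.3 requires a completed six-week visit, waiting for those visits is a fair reading. This stands too: the shortfall in information follows from taking the mid-recruitment wording of section 4.3 as the data cut. What remains is that the protocol does not say which is meant.

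A reader might infer more in two places. Section 10.1 has the monitoring board meet at least yearly "to independently assess safety, effectiveness and futility of the trial", which could be taken as extra efficacy looks. But that text gives a remit, sets no test or threshold, and defers operation to a charter; section 4.3 says the look is one-time. No further inflation can be charged to it, and no restriction of the board's remit follows. Likewise, termination on rejection could be read as cutting off six-month follow-up. But section 4.10.5 has all participants complete the study at six months, so this is at most a wording point to reconcile.

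**Conclusion.** The concern holds in a limited form. The levels in section 9.4 do not keep the two-sided 5%: at exactly half the information the overall error is 5.13%, which needs no assumption beyond the standard bivariate normal approximation. The excess of 0.13 percentage points would change a conclusion only for a result near the boundary.

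The timing part is conditional. If enrollment of the 700th woman is the data cut, and accrual is even over 12 to 24 months (assumed), the error is about 5.16% to 5.22%. If the look waits for six-week results, it adds nothing. The documents do not support a claim of serious inflation of the type I error.

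**What to change.** Either of two changes is enough:

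- In section 9.4 replace 0.0054 and 0.0492 by 0.0052 and 0.0480, change 0.0492 to 0.0480 in section 4.3, and state that the look is taken when half of the planned six-week hemoglobin results are available.
- Or name a Lan-DeMets O'Brien-Fleming-type spending function, define the information fraction as six-week results available over those planned, and compute both boundaries from the actual fraction. At one half this gives 0.0031 and 0.0490. This option is safer if the look may fall away from one half.

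In the same edit, make sections 4.3 and 9.4 describe the timing alike, correct the cross-reference in section 4.3 (it sends the reader to 9.3, but the rule is in 9.4), and reconcile the termination sentence with section 4.10.5.

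The cost is wording in the protocol and in any dependent analysis plan or charter, plus a slightly stricter final threshold. The power lost is 0.2 to 0.3 of a point on the figures above. Restate the power at 700 per arm; five more women per arm are not worth enrolling. The change should be made before any unblinded interim data are seen.

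### The sample-size interim is called blinded but aims at the actual effect size, which pooled data cannot show; if N is re-set on the contrast instead, the final 0.0492 test does not cover it

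*Protocol*

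**What the plan says.** Section 9.4 of the protocol describes two interim analyses.

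The first is for efficacy: "Interim analysis will be conducted after achieving half of the sample size". Its boundary is that "the threshold for significance of the primary endpoint at the interim analysis will be alpha = 0.0054", with the consequence that "The clinical trial is terminated if the null hypothesis is rejected". For the final test, "The alpha level for the analysis at the end of the study will be adjusted to 0.0492". Tests are two-sided.

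The second closes the section: "Interim analysis will also be performed to adjust the sample size, if necessary, as part of an adaptive study design". The protocol then says: "This will be a blinded analysis and its aim is to determine the actual effect size of the primary outcome", to allow a change of sample size. On who does it: "This will be performed by an independent body, and not the study co-investigators".

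The same section defines the primary effect as IV versus oral iron on anemia at six weeks, reported as a relative risk. Section 4.3 plans 90% power for a control rate of 39%. It describes the target both as a 20% relative reduction and as a fall to 30%. It allows 10% loss and arrives at 697 per arm, raised to 700 per arm for the interim look.

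**The concern.** An effect size is a comparison between arms. Someone who sees only pooled data cannot estimate it, so the step cannot be carried out as described. One half of the sentence must give way, and the protocol does not say which.

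The choice matters. If blinding is kept, the review can use the pooled event rate and the loss to follow-up, and the final test is essentially unaffected. If the aim is kept, the total N becomes a function of the observed treatment difference. The levels 0.0054 and 0.0492 were set for one efficacy look in a trial whose final size does not depend on that difference, so the error rate of the single primary test would then rest on a rule that those levels do not cover.

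**Working it through.** **1. What pooled data show.** With 1:1 allocation the pooled rate is the mean of the two arm rates. The planned 39% and 30% (section 4.3) pool to (39 + 30)/2 = 34.5%. So do 34.5/34.5 (no effect), 36.5/32.5, 42/27 and 44.5/24.5. One pooled rate fits a difference of 0 and a difference of 20 points equally well.

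**2. The plan's own boundaries, N fixed.** Critical values: z = 2.782 for 0.0054 and z = 1.967 for 0.0492, both two-sided. With the look at half the information, the two statistics have correlation √0.5. Overall type I error = 1 − P(|Z1| < 2.782 and |Z2| < 1.967) = 0.0513. This is the baseline for step 3. The step from 697 to 700 per arm also reproduces: [(1.967 + 1.282)/(1.960 + 1.282)]² = 1.0043, and 697 × 1.0043 ≈ 700.

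**3. If N is re-set on the observed contrast.** The protocol gives no rule and no timing for this interim, so both are assumed: the look is at half information, and N only rises, to give 90% power at the observed effect. In units of stage-1 information (plan = 2), the new total is T = [(1.967 + 1.282)/|Z1|]², held between 2 and 2 × cap. The final statistic is Z = [Z1 + √(T − 1)·Z*]/√T, with Z* the independent stage-2 statistic. Reject if |Z1| ≥ 2.782 or |Z| ≥ 1.967. Integrating over Z1 under the null:

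| Cap on N | Type I error | Excess over 0.0513 |
|---|---|---|
| 1.25 × plan | 0.0537 | 0.002 |
| 1.5 × plan | 0.0556 | 0.004 |
| 2 × plan | 0.0586 | 0.007 |
| 3 × plan | 0.0623 | 0.011 |

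Sensitivity to the rule:
- Aiming for 90% conditional power gives 0.0568, 0.0601 and 0.0640 at caps of 1.5, 2 and 3.
- Increasing only when the trend favors IV iron gives 0.0525 to 0.0568 for caps of 1.25 to 3.
- Increasing only when conditional power is at least 50% gives 0.047 to 0.049, so no inflation.

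**4. If the review is truly blinded.** Re-sizing on the pooled rate with a 9-point difference held fixed gave simulated type I error of 0.0506 to 0.0517 (400,000 runs at each of four rates). That is the same as the 0.0513 baseline within simulation error.

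**5. If the contrast is used with fixed stage weights.** An inverse-normal combination with the stated boundaries gives 0.0513 whatever the new N. With exact two-look O'Brien-Fleming levels (0.0052 and 0.0480) it gives 0.0500.

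**6. Which target a blinded review would hold.** Section 4.3 offers two: 39% to 30%, or 39% × 0.80 = 31.2%. Two-proportion formula, two-sided 0.0492, 90% power, 10% loss:
- 9-point difference at pooled 34.5% (39% v 30%): 587 per arm, 587/0.9 → 653, total 1,306.
- RR 0.80 at pooled 34.5% (38.3% v 30.7%): 810 per arm, 810/0.9 = 900, total 1,800.

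The stated 697 matches neither target exactly; it comes out at an intervention rate of about 30.3%.

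**The case against.** The protocol says outright that the analysis is blinded and gives it to an independent body. On that footing, effect size may be loose wording for the event-rate assumption, and step 4 shows no added error. A reader might infer that the plan prescribes an unblinded, effect-driven change of N, or that the false-positive rate is certainly inflated. The text supports neither: it calls the step blinded, it states no rule, and some rules inflate nothing. This part of the objection stands and limits the point to a contradiction with a conditional harm.

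Blinded could also mean that arms are coded A and B. The contrast can then be seen, but the review is comparative and step 3 applies. The independent body limits operational bias; it does not change the distribution of the final statistic.

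The re-sizing rule, the cap and any combination test commonly sit in a SAP or charter, and section 10.1 defers DSMB operation to a charter. Their absence is not held against the protocol. No later document, however, can make both halves of the sentence true on the ordinary meaning of blinded.

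A reader might also fear that a revised N would let sites work out the interim result in this open-label trial. That needs a disclosed effect-based formula, and the protocol contains none.

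**Conclusion.** The point holds as an internal contradiction in section 9.4: a pooled review cannot determine the between-arm effect. It should be corrected before the interim is run.

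The statistical consequence is conditional. If N is re-set on the contrast and the final test stays at 0.0492, two-sided type I error is about 0.056 to 0.062 for caps of 1.5 to 3 times the plan, against about 0.051 with N fixed. That rests on an assumed increase-only rule at half information that re-powers on the observed effect. Other rules give somewhat more, less or no inflation. The 0.0054 and 0.0492 levels do govern the efficacy look, approximately; what they do not cover is a change of N driven by the observed effect.

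**What to change.** First, make section 4.3 name one target effect: 39% to 30%, or a 20% relative reduction to 31.2%. This has to come first. If the review held RR 0.80 fixed, it would call for about 1,800 women instead of 1,400 even when the pooled rate came out exactly at the planned 34.5%.

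Then replace the sentence in section 9.4 with wording such as: *A blinded re-assessment of sample size, by a statistician without access to allocation, will use only the pooled six-week anemia rate and the loss to follow-up. The target effect named in section 4.3 stays fixed.* State whether that target is held as a difference or as a ratio, and keep this review separate from the unblinded DSMB efficacy look.

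If re-sizing on the observed effect is really wanted, call it unblinded and pre-specify the rule, the cap and an inverse-normal combination test with stage weights fixed in advance.

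Cost: wording in the protocol and the DSMB charter. A pooled review can no longer react to the observed treatment effect.
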